The study will be a randomized, controlled clinical evaluation of class I and class II dental fillings in a single patient using one restorative materials: F-Composite 2 (Ivoclar Vivadent) placed with a dental adhesive Excite F (Ivoclar Vivadent) in a total-etch mode. This data will be compared to previously placed restorations in the first part of this study which compared two groups: Flash Composite (Ivoclar Vivadent) placed with a dental adhesive Excite F (Ivoclar Vivadent) in a total-etch mode and a commercially available dental composite, Tetric EvoCeram (Ivoclar Vivadent) placed with a dental adhesive Excite F (Ivoclar Vivadent) in a total-etch mode. One restoration will be placed in subjects with carious teeth or defective posterior restorations needing replacement. The study will be conducted in the Department of Clinical and Community Sciences, University of Alabama at Birmingham (UAB), School of Dentistry clinical research clinic. 60 restorations in adult subjects aged 19 years or older will be recruited into the study. Based on previous clinical trials, the average subject attrition rate at the three year recall is approximately 20%. To achieve 50 restorations per group at the three year recall, 60 restorations will be placed assuming a 20% drop out rate.

Investigators

[name] will act as the Principal Investigator and will conduct the calibration exercises. Four experienced operators will place the restorations in the study (Drs. [name], [name], [name], and [name]). All operators will place the same percentage of the restorations. One calibrated operator ([name]) will complete the baseline, 6 month, 1, 2, and 3 year recall examinations. Baseline evaluations will be conducted approximately one week after the restorations are placed.

Background and Significance

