Restorations will be placed in Class I and Class II preparations in molars and premolars. All restored teeth will have natural teeth, crowns or bridgework as antagonists. For the clinical evaluation of the restorations, the criteria listed in Appendix 3 will be used to evaluate the restorations directly and indirectly.

Distribution of Restorations

Each patient must need at least 1 restoration, however, 2 restorations can be placed if that patient has more lesions. A minimum of 75% of the restorations will be class II, and the remainder may be class I restorations with approximately 75% molars and 25% premolars. Four clinicians will insert 60 restorations to have presumably at least 50 restorations available for the 3 year recall.

Size of Cavities

Moderate-large cavities with an isthmus width greater than 1/3 the intercuspal distance (1/3 the distance between the cusp tips) will be selected for this study.

Patient Population

Subjects for this investigation will be selected from subjects of the Dental School at the University of Alabama in Birmingham. Fifty subjects ranging in age from 19 to 90 years will be recruited for this study, about 50% women and 50% men.

Inclusion Criteria

- Each subject must need at least 1 restoration in a vital posterior tooth
- Must have given written consent to participate in the trial
- Replacement of defective restorations (ie fractured, stained, unaesthetic) with or without caries are acceptable
- Must be available for the required three year follow-up visits
- Restored teeth must have occlusal contact with opposing teeth or restored teeth
- Restoration width should be equal to or greater than 1/3 the distance from buccal to lingual cusp tips
- 75% of the restorations Class II (minimum) and 25% Class I
- Each Class II will have at least one proximal contact
- 75% in molars (minimum) and 25% in premolars
- All restored teeth must have at least one occlusal contact in habitual closure
- Must have 20 or more teeth

Exclusion Criteria

- If they have an allergy against ingredients of the materials under investigations (monomers)
- Do not meet all inclusion criteria above
- Have severe medical complications (organ transplants, long term antibiotic or steroid treatment, cancer or immunocompromised) or disabilities who may not be able to tolerate the time required to complete the restorations or to provide adequate oral hygiene

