- Have xerostomia either by taking medications known to produce xerostomia or those with radiation induced or Sjögren's syndrome subjects since dry mouth increases tooth and restoration wear as well as the development of caries.
- Have teeth with advanced or severe periodontitis or rampant caries or poor oral hygiene which may require extraction of the teeth to be restored
- Present with any systemic or local disorders that contra-indicate the dental procedures included in this study
- Have an unstable occlusion
- Have severe bruxing or clenching or need of TMJ related therapy
- Have tooth with exposed pulp during preparation or caries removal
- Teeth that are non-vital or that exhibit signs of pulpal pathology for restoration
- Teeth that require cuspal build-ups involving more than one cusp

Screening

Each subject will be screened for compliance with the inclusion/exclusion criteria specified above. Subjects will be given the consent form and after careful reading any questions will be answered. We will additionally explain any terms, phases or descriptors the subject may not understand. After signing the consent form they will receive a copy of the form.

Risks to the Patient

Subjects will wear lead aprons as a protective measure during the radiographic procedure to minimize risk. Patient data will be monitored and if, during the course of the study, it becomes apparent that any restorative material has poor performance the patient will be informed and if needed the restorations replaced without any costs for the patient.

Consent

Consent for this study will be obtained prior to the initial examination and the initiation of any portion of the study. The PI or Co-investigator will explain the consent to the patient and answer questions they have. The consent forms and all records associated with this study will be maintained in the clinical research office (Room 610) under lock to ensure the records are confidential. Each subject will provide written consent to participate in this study in accordance with Federal regulations (21 CFR Parts 50 and 56).

Materials and Methods

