One dental filling will be placed and evaluated in this study. The F-Composite 2, optimized for bulk placement (up to 4mm increments) and three second polymerization will be evaluated. It will be used with the bonding agent Adhese Universal (Ivoclar Vivadent) in a total-etch mode. All restored teeth will be in occlusion and at least one proximal surface of each class II restoration will be in contact with an adjacent tooth. Cavity preparations will be made the same way for all restorations following rubber dam isolation. A pre-operative photograph will be taken of all teeth in the study.

The experimental material will be cured with the prototype (Bluephase PowerCure) of a new curing device (3,400mW/cm²).

Data Analysis

The categorized clinical assessment (data see above) will be summarized by computing percentages for each category and used to describe any trends noted in the performance of the groups. In the analysis of categorical data of surface luster, surface staining, color match, material fracture, occlusal wear, tooth integrity, caries, marginal adaptation, marginal staining, contact point, post-operative hypersensitivity, patient's satisfaction, and radiographic examination, the frequency distribution over various categories will be calculated and reported. A sample size of 60 subjects is not based on a statistical plan, but rather on guidelines put forth by the American Dental Association.

APPENDIX 1
SCHEDULE OF EVENTS

Procedure	Screening	Preparation	Baseline	6 month	1 year	2 year	3 year
Preoperative radiograph	X						
Subject assignment #	X						
Preoperative sensitivity	X						
Preoperative photograph		X					
Photograph of cavity preparation		X					
Treatment		X					
Photograph	X	X	X	X	X	X	X
Direct Assessment							
Surface Luster			X	X	X	X	X
Surface Staining			X	X	X	X	X
Color Match			X	X	X	X	X
Material Fracture			X	X	X	X	X
Occlusal Wear			X	X	X	X	X
Tooth Integrity			X	X	X	X	X
Caries			X	X	X	X	X
Marginal Adaptation			X	X	X	X	X
Marginal Staining			X	X	X	X	X
Contact Point			X	X	X	X	X
Sensitivity			X	X	X	X	X
Patients View			X	X	X	X	X
Post-op Sensitivity			X	X	X	X	X
Radiographic examination	X					X	X
Indirect Assessment							
BW Radiograph	X					X	X
PA Radiograph (if necessary)			(X)	(X)	(X)	(X)	(X)
Complaints			X	X	X	X	X
Adverse events			X	X	X	X	X
Unanticipated Advers			X	X	X	X	X

Effects							
---------	--	--	--	--	--	--	--

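### Patients and teeth are chosen with the material already known and no selection rule, so selection on depth or difficulty could affect the F-Composite 2 side of the comparison alone

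*Combined protocol and SAP*

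**What the plan says.** Study Design opens with "The study will be a randomized, controlled clinical evaluation", but then describes "class I and class II dental fillings in a single patient using one restorative materials: F-Composite 2 (Ivoclar Vivadent"), and Materials and Methods likewise names F-Composite 2 as the only material to be evaluated. The comparison groups, Flash Composite and Tetric EvoCeram, come from part 1: "This data will be compared to previously placed restorations in the first part of this study which compared two groups". No sequence, concealment or allocation step is described.

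On entry to the study, Patient Population says "Subjects for this investigation will be selected from subjects of the Dental School". Size of Cavities likewise has moderate to large cavities selected. Distribution of Restorations adds "Each patient must need at least 1 restoration, however, 2 restorations can be placed if that patient has more lesions". It also sets a minimum of 75% Class II and about 75% molars. It does not say which lesion is taken when several qualify, or when a second one is added.

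Exclusion Criteria includes "Have tooth with exposed pulp during preparation or caries removal", which can be known only once treatment has begun. Data Analysis plans percentages per category. It contains no account of teeth screened or dropped, and no matching or adjustment to part 1.

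**The concern.** In a concurrent randomized comparison, choosing teeth before allocation affects all groups alike. Here there is one material and the comparators are already in place, so the choice of patient, lesion and second tooth shapes only the new group, and it is made by people who know what that group receives.

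Study Objectives names post-operative hypersensitivity, pulp integrity and restoration survival as primary outcomes. Cavity depth and closeness to the pulp plausibly influence at least the first two. Depth also matters to the product claim, which is a single increment of up to 4 mm cured in 3 seconds. The width criterion and the Class II and molar quotas limit tooth type and cavity size but leave depth free. If deep or difficult teeth were passed over, the F-Composite 2 rates would fall without any effect of the material, and descriptive percentages set beside part 1 could not separate the two.

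**Working it through.** The plan gives no figure for this point. Data Analysis says that the sample size has no statistical basis, so there is no alpha, power or margin to reproduce. The check has three parts.

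**1. How many second teeth are at stake.** Distribution of Restorations plans 60 restorations and Patient Population plans fifty subjects. With at most two per subject, 60 − 50 = 10 second teeth, or 10/60 = 17% of restorations. Data Analysis speaks instead of 60 subjects, and Study Design of one restoration per subject; on those figures there would be none. The choice of patient and first lesion remains open either way.

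**2. How far selection could move a rate (all rates assumed, none in the documents).** Let 20% of eligible teeth be deep with 30% hypersensitivity, and the other 80% have 10%.

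- No selection: 0.2 × 0.30 + 0.8 × 0.10 = 0.140.
- A fraction *a* of deep teeth passed over: rate = [0.2(1 − a) × 0.30 + 0.8 × 0.10] / [0.2(1 − a) + 0.8].
- a = 0.25: (0.045 + 0.080)/0.95 = 0.132, a fall of 0.8 points, or about 0.5 events in 60.
- a = 0.50: (0.030 + 0.080)/0.90 = 0.122, a fall of 1.8 points, or about 1.1 events in 60.

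A second set of assumptions takes 30% to 50% of teeth as high-risk, with event rates of 15% to 20% in those and 3% to 5% in the rest. Passing over half of the high-risk teeth then lowers the rate by 1.5 to 2.5 points. At the upper end, 0.5 × 0.20 + 0.5 × 0.05 = 12.5% becomes (0.25 × 0.20 + 0.5 × 0.05)/0.75 = 10.0%, or 7.5 against 6.0 expected events in 60.

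**3. Against sampling error.** At 14% and n = 60, treated as independent, the standard error is √(0.14 × 0.86/60) = 0.045, or 4.5 points. The shifts are smaller than this. Unlike sampling error, they would not shrink if more teeth were placed.

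**The case against.** The best defense is that this is ordinary enrollment discretion, already narrowed by the size criterion and the quotas, and that any preference for manageable teeth may have operated in part 1 as well. If so, it would cancel in whole or in part. This stands: the documents do not give part 1's selection rules, so a bias toward F-Composite 2 cannot be asserted. Excluding pulp exposures is likewise neutral if part 1 did the same.

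Four stronger readings are tempting, and the documents do not support them.

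- A reader might infer that cavity width is a second criterion settled once the tooth is open: "Restoration width should be equal to or greater than 1/3 the distance from buccal to lingual cusp tips". The plan does not say when width is judged, and Screening has subjects checked against the criteria beforehand. The criterion is also a minimum, so applying it late would remove small cavities, not deep ones.
- A reader might infer that dropped teeth would be invisible. Consent precedes the initial examination, and Appendix 1 schedules a subject number, radiograph and preoperative sensitivity at screening, so a subject lost at preparation already has records. What is missing is a requirement to report such losses and any list of teeth never chosen.
- A reader might infer that depth goes unrecorded. Appendix 1 schedules radiographs and a photograph of the cavity, and Study Objectives plans casts of the preparations. Depth is at least partly recoverable for teeth that enter.
- A reader might infer that deep teeth carry most of the risk and quote the extreme case. In the illustration they supply 0.06/0.14 = 43% of events, and the largest shift, 14.0% to 10.0%, requires passing over every one of them.

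**Conclusion.** The point holds as an open opportunity for selection. With a single known material and comparators already in place, nothing in the plan fixes which patient or lesion enters or when a second tooth is added, and nothing requires teeth excluded at preparation to be reported. The documents do not show that selection occurs or that it favors F-Composite 2.

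Under the assumed rates, passing over a quarter to a half of deep teeth moves the result by about 1 to 2 points. That is modest beside a standard error of 4.5 points, but it is systematic. The size rests wholly on assumed depth shares and event rates, and the direction relative to part 1 on rules that are not given. The change is worth making because it costs little and unrecorded choices cannot be reliably reconstructed later.

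**What to change.** Keep the eligibility criteria as they are and add the following.

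1. Enroll consecutive eligible, consenting patients from a dated screening log.
2. List all eligible teeth at screening. Where there are more eligible teeth than study places, choose by a pre-drawn random order within the Class II and molar quotas. State in advance when a second tooth enters, and reconcile the differing statements on restorations per subject and number of subjects.
3. Register each study tooth before preparation starts, and report every registered tooth not restored, with the reason, including pulp exposure.
4. Use the scheduled radiographs and cavity photographs and the planned casts to describe cavity depth. Where part 1 has the same records, set them side by side.
5. State that the comparison with part 1 remains non-randomized. These steps limit selection in this part and make it visible; they do not by themselves make the groups comparable.

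The cost is a log, a random list and some description from records already planned, with no added visit or procedure. Operators lose the freedom to pick the study tooth, though other teeth can still be treated outside the study. If part 1 teeth were chosen by operators, a stricter rule here is itself a difference between the parts and must be acknowledged.

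### Subject and restoration counts contradict each other, no unit of analysis is named although two restorations per patient are allowed, and 60 restorations at 20% attrition leave 48 rather than 50

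*Combined protocol and SAP*

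**What the plan says.** The combined protocol and SAP describes the sample in several places.

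- Study Design, restorations per patient: "One restoration will be placed in subjects with carious teeth or defective posterior restorations needing replacement".
- Study Design, total: "60 restorations in adult subjects aged 19 years or older will be recruited into the study".
- Study Design, loss to follow-up: "the average subject attrition rate at the three year recall is approximately 20" percent. From this it derives 60 placed in order to have 50 per group at three years.
- Distribution of Restorations: one restoration is the minimum, but "2 restorations can be placed if that patient has more lesions". The same section repeats 60 placed and expects at least 50 at the three-year recall.
- Patient Population: "Fifty subjects ranging in age from 19 to 90 years will be recruited for this study".
- Materials and Methods: "One dental filling will be placed and evaluated in this study". This may mean one type of material, so nothing below relies on it.
- Data Analysis: "A sample size of 60 subjects is not based on a statistical plan".

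Data Analysis plans percentages and frequency distributions for each outcome. It names no unit of analysis and does not mention patients who contribute two teeth. Study Objectives nevertheless sets a comparative aim, that the new material should perform the same as the established composite, and makes overall restoration survival a primary outcome.

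**The concern.** A reader cannot tell how many people will be enrolled, how many teeth each may contribute, or what the denominator of each percentage will be.

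Two fillings in one mouth share the patient's hygiene, caries risk and bite, and are lost together if the patient leaves. The protocol accepts that such traits matter: Exclusion Criteria removes patients with dry mouth because it increases wear and caries, and also excludes unstable occlusion, severe bruxing and poor hygiene. Pairs of restorations should therefore be expected to be correlated. Patient satisfaction is also among the tabulated outcomes, and if it is counted per restoration, a patient with two fillings may be counted twice.

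At stake are the number of restorations that will support the three-year result, and the validity of any precision attached to the comparison.

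**Working it through.** **1. The plan's own retention figure.** Inputs from Study Design: target 50, attrition 20%.

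- 50 × 1.2 = 60. This reproduces the stated number placed.
- The correct inflation is 50 / (1 − 0.20) = 62.5, so 63.
- In the other direction, 60 × 0.80 = 48 expected at three years, 2 short of 50.

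**2. Do the counts fit together?** Let s be patients with one restoration and p patients with two.

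- Fifty subjects, 60 restorations: s + p = 50 and s + 2p = 60 give p = 10 and s = 40. This contradicts one restoration per subject and the 60 subjects in Data Analysis.
- Sixty subjects, 60 restorations: p = 0. This contradicts the fifty subjects, and the allowance for two would never be used.
- Fifty subjects with one each: 50 restorations placed, not 60, and 50 × 0.80 = 40 retained.

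No combination satisfies every statement.

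**3. Does pairing change the number retained?** Assume each patient leaves with probability 0.20, whether he or she has one or two restorations.

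- 60 singles: mean 60 × 0.8 = 48; SD = √(60 × 0.16) = 3.1.
- 40 singles and 10 pairs: mean 40 × 0.8 + 10 × 2 × 0.8 = 48; SD = √(40 × 0.16 + 10 × 4 × 0.16) = √12.8 = 3.6.

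The expectation is the same and only the spread grows. By exact binomial calculation, the chance of keeping 50 or more is 0.32 for the singles and 0.35 for the mixed layout.

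**4. Effect of clustering on precision.** The ICC is not in the documents. The range 0.1 to 0.5 is an assumption.

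- Design effect = 1 + (Σm²/Σm − 1) × ICC, where m is restorations per patient.
- For 40 singles and 10 pairs, Σm²/Σm = (40 × 1 + 10 × 4) / 60 = 1.333, so the design effect is 1 + ICC/3.

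| Assumed ICC | Design effect | Interval width ratio (square root) | 48 restorations are worth |
|---|---|---|---|
| 0.1 | 1.033 | 1.02 | 46.5 |
| 0.3 | 1.100 | 1.05 | 43.6 |
| 0.5 | 1.167 | 1.08 | 41.1 |

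For an assumed event rate of 10%, the 95% half-width with 48 independent restorations is 1.96 × √(0.1 × 0.9 / 48) = 8.5 percentage points. Multiplying by the width ratio gives 8.6 points at ICC 0.1 and 9.2 at ICC 0.5.

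**The case against.** The strongest reply is that the plan is descriptive. It states no interval, test, margin or power, and says openly that the sample size has no statistical basis. Percentages of restorations remain valid descriptions when some patients contribute two. This stands. A reader might infer that the plan already overstates its precision, but it states none. The absence of any adjustment is silence about the unit, not a declared assumption of independence.

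A reader might also infer that two restorations per patient is why fewer than 50 will remain. Step 3 shows otherwise: the expected 48 does not depend on the pairing, and the shortfall comes from the inflation formula. It is only 2 restorations, against an attrition rate that the protocol itself calls approximate.

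Two more alarming figures are also unsupported.

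- Losing 10 of 50 subjects could in principle leave anything from 40 to 50 of the 60 restorations. The value 40 requires all ten dropouts to be the ten paired patients. With random dropout the number of pairs lost has mean 2, and 46 to 50 restorations remain with probability about 98%. This is distinct from the 40 in step 2, which is an expectation under one restoration in each of fifty subjects.
- A layout of 30 patients with two each would double the variance at ICC 1, but no stated headcount is 30.

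Finally, the reference to 60 subjects may be loose wording for 60 restorations. Even so, Study Design still conflicts with Distribution of Restorations on how many each patient may have, and this charitable reading is the one in which 10 patients contribute pairs.

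**Conclusion.** The contradiction in the counts is certain and can be read directly from the text. Its practical range is wide: the implied three-year number is about 48 if 60 restorations are placed, and about 40 if fifty subjects receive one each.

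The unit of analysis is unspecified. The consequence is conditional and modest: intervals that ignored the patient would need to be about 2% to 8% wider in the 50-subject, 60-restoration layout, and no wider if each patient has one restoration. This rests on the assumed ICC of 0.1 to 0.5, on dropout unrelated to the number of restorations, and on the new material's group alone. It matters because a judgement that two materials perform the same needs some measure of precision, and precision needs a stated unit.

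The expected retention of 50 is an arithmetic slip. At the stated attrition it should be about 48 of 60.

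**What to change.** - State one number of subjects, one number of restorations and one maximum per patient, identically in Study Design, Distribution of Restorations, Patient Population, Materials and Methods and Data Analysis.
- Restate expected retention as about 48 of 60. If 50 is a real requirement, the number to place at 20% attrition is 63.
- In Data Analysis, name the restoration as the reporting unit and the patient as the cluster, and say how patient satisfaction is counted when a patient has two restorations.
- If two per patient are kept, use patient-clustered intervals (GEE or cluster-robust variance, including for survival) for any reported precision or comparison. Add a sensitivity analysis with one restoration per patient, for example the first placed. If the maximum is set at one, none of this is needed.
- Report attrition both by patient and by restoration.

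This costs protocol and analysis wording only, with no extra visits or data unless 63 are placed. The price is slightly wider intervals and a slightly lower stated retention figure.

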The impetus for bulk-filling composites is driven by a desire to reduce the time required for composite placement and eliminate the possibility of voids between composite layers. The time savings allowed by placing a single layer of composite can be appreciated by both the dentist and the patient receiving the treatment. Additionally, an unwanted side effect of the incremental placement technique is the introduction of voids between composite layers. For universal handling composites, the stickiness of the composite to the placement instrument can make it difficult to completely adapt the new layer of composite to the previous layer. When placing additional layers of flowable composite, air can become entrapped between layers. Internal voids may be innocuous in some clinical cases, however, in stress bearing areas, a void may act as a site of stress concentration and eventual fracture.² Voids or gaps present on the external surface of a composite restoration may be more prone to staining.

Purpose

This randomized, controlled, prospective clinical trial will compare the clinical success of a new formulation of an ultra-rapid polymerization time bulk-fill composite ("F-Composite 2", Ivoclar Vivadent) with a bonding agent, to a previous formulation of the same material and a commercially successful dental composite (Tetric EvoCeram, Ivoclar Vivadent, Buffalo, NY) for surface luster, surface staining, color match, material fracture, occlusal wear, tooth integrity, caries, marginal adaptation, marginal staining, contact point, post-operative hypersensitivity, patient's satisfaction, and radiographic examination (pre-operative and at 3 years) using modified FDI criteria. The three year clinical evaluation will evaluate the restorations using direct and indirect methods. Digital images will be made of each restoration and stored by patient if acceptable to patient and deemed clinically necessary.

Study Objectives

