The purpose of this randomized controlled clinical trial is to compare the clinical success of a new formulation of a composite with an ultra-rapid polymerization time (F-Composite 2, Ivoclar Vivadent) to a commercially successful nanohybrid composite (Tetric EvoCeram, Ivoclar Vivadent, Buffalo, NY) and a previous formulation of the material ("Flash Composite", Ivoclar Vivadent) placed in Class I and Class II cavities in permanent teeth. The F-composite 2 material is a newly developed material from Ivoclar Vivadent. The objective of the study is to determine whether a simplified placement procedure of the F-composite 2 in a single increment of at most 4mm with a reduced amount of time of light polymerization (3 seconds) yields the same results as a widely used commercially available dental composite (Tetric EvoCeram). The new procedure would significantly facilitate and shorten the clinical procedure and potentially reduce voids between layers of composite. The restorations will be evaluated directly in the oral cavity at baseline (1

week), 6 months, 1 year, 2 years, and 3 years using modified FDI criteria. Casts made from impressions of the preparations will be analyzed to verify anatomic form and marginal integrity. Primary clinical outcome measures are frequency of post-operative hypersensitivity, pulp integrity, and the overall survival rate of the restorations in relation to the material. The secondary outcome measures of the study are surface luster, surface staining, color match, material fracture, occlusal wear, tooth integrity, caries, marginal adaptation, marginal staining, contact point, patient's satisfaction, and radiographic examination.

Ethical Standards

The study will be conducted in accordance with the Declaration of Helsinki (1964) as revised in Venice in 1983. Institutional Review Board approval has been obtained prior to commencing the study. Informed written consent will be obtained from all subjects prior to registration for participation in the evaluation. Implicit in giving informed written consent, each patient reserves the right to withdraw from the study at any time (See consent form).

Study Design

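### The protocol names two different adhesives for F-Composite 2; under the Materials and Methods version, adhesive and composite cannot be separated in the comparison with part one

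*Combined protocol and SAP*

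**What the plan says.** Only F-Composite 2 is placed in this study. The comparators come from part one: "This data will be compared to previously placed restorations in the first part of this study which compared two groups".

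The adhesive is specified in two places.

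- **Study Design**, for the new material: "F-Composite 2 (Ivoclar Vivadent) placed with a dental adhesive Excite F (Ivoclar Vivadent) in a total-etch mode". The same section describes the part-one groups as "Flash Composite (Ivoclar Vivadent) placed with a dental adhesive Excite F (Ivoclar Vivadent) in a total-etch mode" and "Tetric EvoCeram (Ivoclar Vivadent) placed with a dental adhesive Excite F (Ivoclar Vivadent) in a total-etch mode".
- **Materials and Methods**, where the sentence before it is about F-Composite 2: "It will be used with the bonding agent Adhese Universal (Ivoclar Vivadent) in a total-etch mode".

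The Purpose section mentions a bonding agent without naming it, so it does not settle the matter. Study Objectives sets the primary outcomes: "Primary clinical outcome measures are frequency of post-operative hypersensitivity, pulp integrity, and the overall survival rate of the restorations in relation to the material". Data Analysis plans percentages by category and does not mention the adhesive. The schedule of events in Appendix 1 has a treatment entry but no item recording which adhesive was used.

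**The concern.** These are two differently named products, given for the same component of the only treatment being placed. One of the two sections must be wrong.

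If the Study Design text is right, the adhesive is common to all three groups. If the Materials and Methods text is right, the adhesive changes together with the composite, and the stated objective does not declare that second change. The objective is about the composite and its simplified placement: one increment of up to 4 mm and a 3-second cure.

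The adhesive acts at the bonded interface, which is what marginal adaptation and marginal staining assess and where post-operative hypersensitivity may arise. A difference from part one could come from the adhesive. An apparent similarity could also hide offsetting effects, which matters because the objective asks whether the new procedure gives the same results as Tetric EvoCeram.

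**Working it through.** The plan gives no figure to reproduce here. The check sets the text side by side and then asks what the comparison can estimate.

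**Adhesive by group, as written (all total-etch)**

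| Group | Placed in | Study Design | Materials and Methods |
|---|---|---|---|
| Tetric EvoCeram | part one | Excite F | not stated |
| Flash Composite | part one | Excite F | not stated |
| F-Composite 2 | this study | Excite F | Adhese Universal |

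The part-one adhesive comes from Study Design in either case, because no other section gives it.

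**Overlap if Materials and Methods governs.** Adhese Universal is used in 60 of 60 new restorations and in none of the comparators. No composite is observed with both adhesives.

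**What can be estimated.** Take Tetric EvoCeram with Excite F as reference and write the expected outcome as

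a + b·(F-Composite 2) + c·(Flash Composite) + d·(Adhese Universal).

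*Materials and Methods version*

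- Tetric EvoCeram: a
- Flash Composite: a + c
- F-Composite 2: a + b + d
- F-Composite 2 minus Tetric EvoCeram = b + d
- F-Composite 2 minus Flash Composite = b + d − c

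b and d appear only as a sum. In the design matrix, the Adhese Universal column equals the F-Composite 2 column in every row, so the rank is 3 for 4 columns. The rank depends on which combinations occur, not on how many restorations there are, so a larger sample changes nothing.

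*Study Design version*

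- The adhesive column is zero in every row and drops out.
- The remaining three columns have rank 3, so every contrast between composites is estimable as far as the adhesive is concerned.
- F-Composite 2 minus Tetric EvoCeram = b
- F-Composite 2 minus Flash Composite = b − c

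**If operators read different sections.** Suppose k of the 60 new restorations receive Adhese Universal. The contrast with Tetric EvoCeram becomes b + (k/60)·d. Four operators with equal shares place 60/4 = 15 restorations each. As an illustration, one operator following Materials and Methods and three following Study Design gives k/60 = 15/60 = 25%. With no adhesive field, k would not be known from the study data.

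**What reconciling the adhesive does not do.** Part one was carried out earlier, so a period effect p enters both versions: b + d + p under Materials and Methods, b + p under Study Design. Using Excite F throughout removes d and leaves p.

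**The case against.** The strongest reply accepts the contradiction but disputes its reach.

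- **The confounding is conditional.** It exists only if Materials and Methods governs. That is correct, and the claim is limited to that case. The contradiction itself does not depend on it.
- **The comparison is not clean anyway.** The comparators are historical, and the experimental material is cured with a prototype light at 3,400 mW/cm². This stands: correcting the adhesive does not make a pure composite effect identifiable. But the short cure is part of the procedure under test, whereas a change of adhesive appears nowhere in the objective and is avoidable.
- **The objective is already partly about a procedure or system.** The phrase "the overall survival rate of the restorations in relation to the material" attaches most directly to survival, and the Purpose section includes a bonding agent in the test arm. This is fair. It makes any restatement of the objective modest, but does not say which adhesive belongs to the system.
- **The documents do not show that the adhesives perform differently.** They are from one manufacturer and used in the same etch mode. This also stands: the direction and size of d are unknown, so no bias can be quoted.
- **The analysis is descriptive, and mixed use by operators is speculative.** With no formal test planned, the harm lies in interpretation, and accurate reporting of the adhesive would limit it. Nothing indicates that operators would in fact diverge. Neither point removes the need for a single instruction.

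**Conclusion.** The concern holds. The protocol gives two incompatible adhesive instructions for the material under test, and the available text does not resolve them. This should be corrected before restorations are placed.

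Under the Materials and Methods version the aliasing is complete: 60 of 60 new restorations against no comparators with Adhese Universal, so only b + d can be estimated. Under the Study Design version this aliasing is absent.

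The conclusion assumes that part one used Excite F throughout, as Study Design reports, and that each instruction is applied as written. It does not assume that the adhesives perform differently, and it does not say which section is correct. The historical comparators are a separate limitation that remains either way.

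**What to change.** 1. Decide which adhesive is used with F-Composite 2 and state it identically in Study Design and Materials and Methods before any placement.
2. Add a case-record field for the adhesive used in each restoration, and report it by group.
3. If the adhesive differs from part one, restate the objective and conclusions as a comparison of composite-plus-adhesive systems, and do not attribute results to the composite alone.
4. If placement has already taken place, state which adhesive each restoration received and word the conclusions to match.

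The cost is two aligned sentences and one data field. If the adhesives differ, the permitted conclusion is narrower.
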